1 PROTOCOL SUMMARY

1.1 SYNOPSIS			
Title:	RANDOMIZED DOUBLE-BLIND PLACEBO-CONTROLLED PROOF-OF-CONCEPT TRIAL OF RESVERATROL FOR THE OUTPATIENT TREATMENT OF MILD CORONAVIRUS DISEASE (COVID-19)		
Study Description:	•	trial to determine the safety and explore the efficacy of using itamin D3 to treat patients with mild COVID-19	
Objectives:	Primary Objective:	To compare the 21-day hospitalization rate among early or mild stage COVID-19 patients taking a 15-day regimen of resveratrol pus vitamin D3 to that for patients taking an identical placebo regimen.	
	Secondary Objectives:	Decrease morbidity and mortality in terms of reduced days of symptoms, reduced rate of ICU admission, reduced rate of mechanical ventilation, and reduced mortality.	
Endpoints:	Primary Endpoint:	Hospitalization rate	
	Secondary Endpoints:	ICU Admission rate, invasive ventilation rates, duration of symptoms, and mortality rates.	
Study Population:	200 hundred patients (100 per group) 45 years and older who test positive for SARS- COV2 who have mild COVID-19 based on WHO Baseline Severity Categorization		
Phase:	2		
Description of Sites/Facilities Enrolling Participants:	Outpatients presenting to COVID-19 testing sites of Mt Carmel Health Systems in Columbus, OH, which may include drive-thru testing centers, emergency departments, urgent care centers.		
Description of Study Intervention:	Patients will be placed on a 15-day course of two 500 mg resveratrol capsules 4 times per day, versus the same dosing frequency of placebo. Both groups will receive 100,000 IU on day one only.		
Study Duration	: up to 6 months		
Participant Duration:	60 days		

1.2 SCHEMA

Prior to Enrollment Screening

•Total n=200

• Review electronic report of newly positive SARS-CoV2 test results of patients 45 and older

- •If old records are available, clinicians to prescreen for exclusion criteria
- •Contact potenially eligible participants by phone to discuss interest in study
- •Patient referred to an online site to review a video discribing the study, risk, benefits.
- Patient given the opportunity to ask questions
- •Obtain informed consent electronically
- •Screen potential participants by inclusion and exclusion criteria
- •Obtain history, document

Randomization

•Intervention Group 1 (n=100)

•Placebo (n=100)

Day1

Baseline Survey & Start treatment

•Patient take Vitamin D3 100,000 IU on day and starts treatment or placebo

• Patients will receive an baseline assessment using Patient-Reported Outcomes version of the Common Terminology Criteria for Adverse Events (PRO-CTCAE[™]).

Day 2-15

Treatment or placebo and daily online survey

•Participant to take 2 capsules of intervention or placebo 4 times per day for 15 days.

• Participant will receive a daily online survey to assess for signs and symptoms of COVID-19 and to report potential side effects. If a patient has not completed an online survey within 24 hours, the patient will be contacted via phone to check their status.

Day 8, 15, 21

Weekly PRO-CTCAE Survey

•Patients will questionnaire with 7 day look back of adverse events based on the Patient-Reported Outcomes version of the Common Terminology Criteria for Adverse Events (PRO-CTCAE[™]).

Between day 21-30 Follow-up assessments for efficacy

•Clinicians will perform a chart review to assess patient outcomes as well as contact patient for an exit interview via phone.

Day 30 and Day 60

Long term assesment

[figure not shown]
• Participant Completes PRO-CTCAE to evaluate for adverse events

Study Completion Follow-up assessments of study endpoints and safety

•Data analysis

• Possible long term follow up of adverse events as outlined in section 8.3

1.3 SCHEDULE OF ACTIVITIES (SOA) Day 1 Results Available

2 INTRODUCTION

2.1 STUDY RATIONALE

Resveratrol (RV) is a polyphenol produced by plants in response to injury or infection. It is found in grapes, peanuts, and other common foods. RV has been associated with a variety positive health effects in areas of inflammation, cardiovascular diseases, cognitive disease, cancer, diabetes, and infectious disease (Tomé-Carneiro, et al., 2013) (specifically including viral diseases (Abba, Hassim, Hamzah, & Noordin, 2015)). RV is readily available commercially as a plant extract and can be produced by genetically engineered yeast (Li, et al., 2015). COVID-19 is the disease caused by a novel coronavirus (SARS-CoV2) that can result in life threatening complications, including lung injury and stroke. While there are numerous trials investigating treatment options, there are no proven effective treatment options. Multiple lines of preclinical data suggest that RV may be effective against coronavirus (See Figure 1).

2.2 BACKGROUND

Coronavirus (CoV) is characterized by surface spike proteins than bind to a region of the Angiotensinconverting enzyme 2 (ACE2) of the respiratory tract. Binding to the ACE2 is required for entry into the affected cell and is dependent upon a transmembrane serine protease (TMPRSS2) (Hoffmann, et al., 2020). After entry into the cell a variety of processes occur, including the down regulation of ACE2 (Kuba, et al., 2005) as well as the subsequent destruction of the pneumocyte. The deficiency in ACE2 caused by SARS is associated with lung injury (Yan, Xiao, & Lin, 2020). Damage to the pneumocyte triggers the release of inflammatory mediators, and the subsequent release of cytokines (IL1, IL6, TNF- α) and reactive oxygen species. While these effects are part of the host defense mechanism, the resultant inflammation is destructive to the alveoli. A "cytokine storm" results in further damage to the alveoli and the development of Acute Respiratory Distress Syndrome (ARDS) (Mehta, et al., 2020).

In addition to ACE2 being a binding site for CoV, it is also associated with protective effects in SARS induced lung injury (Nicholls & Peiris, 2005) (Gu, et al., 2016). ACE2 may attenuate vascular permeability, inflammatory cell infiltration, pulmonary edema, hyaline membrane formation, and prevent acute lung injury (Yan, Xiao, & Lin, 2020). RV has been shown to upregulate ACE2 (Moran, et al., 2017). The upregulation of ACE2 by RV may provide protective effects in COVID-19 (Imai, et al., 2005) (Yan, Xiao, & Lin, 2020) (Magrone, Magrone, & Jirillo, 2020).

RV's antiviral, anti-inflammatory, and antioxidant properties may be helpful in reducing the clinical effects of COVID. (See Figure 1). RV has demonstrated antiviral effects in a variety of animal and human disease (Abba, Hassim, Hamzah, & Noordin, 2015). Specific to CoV, in vitro studies demonstrate that RV inhibits MERS-CoV infection by decreasing nucleocapsid protein resulting in reduced viral production and increased cell survival. (Lin, et al., 2017). Starting at the first steps in the infection *in silico* modeling suggests that RV may interfere with the binding of CoV spike protein to the ACE2 receptor (Wahedi, Ahmad , & Sajjad , 2020) (Rane, Chatterjee, Kumar, & Ray, 2020). RV has been shown to downregulate

TMPRSS2 (Wilson, et al., 2017). Noting that after CoV binds to ACE2, TMPRSS2 may be required to activate cell entry of CoV into the host cell (Shulla, et al., 2011), the downregulation of TMPRSS2 by RV could help reduce the infectivity of the virus. *In silco* analysis also suggests that resveratrol may inhibit COVID-19 RNA Dependent Polymerase and Papain-like Protease (El-Aziz, Shehata, Awad, & El-Sohaimy, 2020) (Ranjbar, Jamshidi, & Torabi, 2020) which could explain the inhibition of nucleocapsid protein described by Lin et al 2017. In silico analysis also demonstrates potential inhibition of the coronavirus main proteinase (Mpro) (Mishra, Pathak, & Tripathi, 2020) which would be additional mechanism of inhibiting viral replication.

Coronavirus is associated with the potential for excessive inflammation. CoV has been shown to activate Toll-Like Receptor 4 leading to an unbalanced inflammatory response and damaging inflammation (Olejnik, Hume, & Mühlberger, 2018). RV has been demonstrated to inhibit TLR4 activation (Sun, et al., 2018). CoV has been shown to increase pro-inflammatory cytokines IL-1, IL-6 (Conti, et al., 2020), CCL5 (RANTES) (Patterson, et al., 2020) and TNF-α (Wang, et al., 2007). Suppression of inflammation has been shown to be therapeutic in a variety of illnesses. RV has been shown to reduce inflammation via a variety of mechanisms (Zhu, Lei, & Dong, 2017) including decreasing the release of inflammatory cytokines in the macrophages of patients with COPD (Culpitt, et al., 2003). RV has also been shown to inhibit the proinflammatory transcription factor NF-κB (Ren, et al., 2013) and inhibition of NF-κB has been shown to increase survival in a mouse model of SARS-COV1 (DeDiego, et al., 2014). The anti-inflammatory effects of RV may be beneficial in mitigating the cytokine storm that is associated with ARDS and high mortality of COVID-19 (Mehta, et al., 2020).

Oxidant stress is associated with viral infections. Inflammatory cytokines trigger the release of reactive oxygen species (ROS). Excessive release of ROS damages both infected as well as healthy cells and may play a role in heart and lung tissue damage in COVID-19. The use of antioxidants has been proposed in the treatment of COVID-19 (Wang & Zhang, 2020). RV's antioxidant properties may provide additional outcome benefits.

[figure not shown]
Prevention of lung injury would be a main treatment goal in COVID-19. The cytokine storm associated is one of the main mechanisms on injury. Therefore, it is notable that a mouse model of cytokine storm showed a 100% mortality reduced to 0% in resveratrol treated mice with minimal lung injury in the treated group (Alghetaa, et al., 2018). Furthermore, the cytokine storm of COVID-19 leads to ARDS. A mouse model of ARDS uses lipopolysaccharide (LPS) as a model of ARDS caused by sepsis (Chen, Bai, & Wang, 2010). RV has demonstrated protective effects in LPS induced lung injury (Hu, Chen, Li, Jiang, & Zhu, 2019) (Jiang, et al., 2016). The proposal by Jaing is RV's inhibition of NLRP3 inflammasomes. Inhibition of NLRP3 inflammasomes in another proposed therapeutic target in COVID-19 (Shah, 2020) (Yap, Moriyama, & Iwasaki, 2020).

As the above discussion regarding RV's effects are largely based on in vitro models of disease, there is always a concern regarding whether in vitro models will translate into in vivo efficacy. Multiple animal studies have shown that RV does improve outcomes in animal models of viral infections. A porcine model of pseudorabies virus shows that piglets inoculated with the virus had no mortality at an orally administered RV dose of 30mg/kg (a dose comparable to an easily achievable human dose) compared to a 40% mortality in the untreated group. Specifically, that study showed alveolar destruction in the untreated group vs mild lung injury in the treated group. The proposed mechanism is inhibition of IkB kinase (Zhao, et al., 2018). It is notable that a drug prediction analysis of SARS-CoV2 suggests that IkB kinase inhibition is a potential target for COVID-19 (Fagone, et al., 2020). Similarly, a murine model of H1N1 influenza showed dose dependent inhibition of viral replication and showed a 60% survival rate in RV treated mice compared to 20% in placebo treated mice (Palamara, et al., 2005). In Respiratory Syncytial Virus infected mice, RV treated mice showed significantly less lung damage compared to untreated mice (Zang, et al., 2011).

Recently, case reports have described an increased risk of stroke associated with COVID-19. This has been attributed to coronavirus attaching to ACE2 receptors of vascular endothelium leading to endothelial injury (Markus & Brainin, 2020) (Akshay Avula, 2020). Excessive complement activation has been proposed as an additional mechanism of thrombotic microangiopathy and complement inhibition has been proposed as an adjunctive treatment to decrease the severity of COVID-19 (Campbell & Kahwash, 2020). RV has been shown to inhibit complement activation in mice (Wu, et al., 2015). Activation of TLR4 by CoV may be the trigger associated with increased Platelet Activating Factor (PAF). RV has been show in inhibit PAF (Shigematsu, et al., 2003) which may be protective in the setting of cerebral ischemia (Lei, Tu, Wang, Tu, & Shi, 2019). RV has been associated with a variety vasoprotective effects (Das & Das, 2010) (Gracia-Sancho, Villarreal, Zhang, & García-Cardeña, 2010). One of the vasoprotective mechanisms reported is increased endothelial nitric oxide (Xia, Förstermann, & Li, 2014). Nitric oxide is an antioxidant and signaling molecule that has been shown to inhibit viral replication, viral protein synthesis, and viral RNA synthesis in SARS-CoV (Åkerström, et al., 2005) (Åkerström, Gunalan, Keng, Tan, & Mirazimi, 2009). These mechanisms may decrease the risk of stroke in COVID-19.

Given the scale of the health and economic impacts of COVID-19, any treatment that can reduce hospitalizations could have a significant impact in this pandemic. RV is generally recognized as safe and has been shown to have positive health benefits in human trials. Prior research in human trials related to lung disease, in vitro studies of RV for coronavirus, and animal studies of RV in other viral infections support investigating RV as a treatment for coronavirus disease (COVID-19) (see summary in Figure 1). Given that RV is readily available and could be cheaply scaled up through the fermentation of yeast, it is potentially a scalable solution to treat coronavirus disease.

2.2.1 FIGURE 1. - SUMMARY OF RESVERATROL EFFECTS ON VIRUS AND HOST

2.3 RISK/BENEFIT ASSESSMENT

2.3.1 SAFETY AND DRUG INTERACTIONS

To characterize toxicity, RV has been dosed at 200mg/kg/day in rats and 600mg/kg/day in dogs with no observed adverse effects (NOAEL) as measured by clinical observations, hematology, ophthalmology, cardiovascular, and neurotoxicity evaluation along with evaluation of organ weights, histopathology and gross pathology (Johnson, et al., 2011).

While human clinical trials have shown RV to generally be safe and well tolerated at doses of up to 5g, dose related gastrointestinal upset has been reported (Ramírez-Garza, et al., 2018). There are some additional concerns of adverse effects based primarily on in vitro studies and animal models (Shaito, et al., 2020). High doses are associated with inhibition of cytochrome P450 (specifically CYP3A4, CYP2D6, & CYP2C9), which could result in some drug interactions, most concerning for drugs with a narrow therapeutic window. Drug interactions with nicardipine, warfarin, HIV protease inhibitors, anti-arrhythmics, calcium cancel agonists, and antihistamines, and immunosuppressants have been reported in animal models (Shaito, et al., 2020). Hydroxychloroquine and chloroquine, drugs with narrow therapeutic window, are being investigated for use in COVID-19, are notably metabolized by CYP2C8 and CYP3A4. With the exception of a patient with multiple myeloma undergoing chemotherapy plus high dose RV who became dehydrated and developed renal failure (cast nephropathy), other studies of RV in humans have not shown adverse effects of hematologic, hepatic, thyroid, and renal functions (Tomé-Carneiro, et al., 2013).

Medication that have been reported in the literature as co-administered medications with resveratrol include amoxicillin, aspirin, atorvastatin, bortezomib, buspirone, caffeine, carbamazepine, cholinesterase inhibitors, dextromethorphan, DHA, EPA, epigallocatechin-3-gallate, inositol, hydroxychloroquine, glibenclamide, lactoferrin, losartan, meloxicam, memantine, metformin, methotrexate, N-acetylcysteine, orlistat, Pegylated-Interferon-α2b, piperine, prednisolone, PUFA, r-tPA (activase), Ribavirin, sulfasalazine, vitamin D3, as well as generic descriptions of the inclusion of "anti-hypertensive drugs," "anti-thrombotics," "beta-blockers," "glucose-lowering drugs," "statins," "NSAIDS," and patient's "usual medications".

Despite the extensive list of medications that have reportedly been co-administered with resveratrol there is little published information about reported adverse events/adverse interactions associated with these co-administered medications. There are multiple reports of benefits/synergistic effects. The 2 most useful references for adverse events and drug interactions are "Drug Interaction Potential of Resveratrol" (Detampel, Beck, Krähenbühl, & Huwyler, 2012) and "Potential Adverse Effects of Resveratrol: A Literature Review" (Shaito, et al., 2020). The source literature that is the basis of concern for CYP interactions is largely based on healthy volunteer studies in "Resveratrol Modulates Drug- and Carcinogen-Metabolizing Enzymes in a Healthy Volunteer Study" (Chow, et al., 2010) and "Effect of

Resveratrol on the Pharmacokinetics of Carbamazepine in Healthy Human Volunteers" (Bedada & Nearati, 2015) which measured an increase in carbamezapine levels when coadminstered with RV.

Of the few relevant clinical trials that mention drug interactions, "Resveratrol Does Not Benefit Patients With Nonalcoholic Fatty Liver Disease" (Chachay, et al., 2014) uses 1500mg BID and states "Previous reports have discussed the potential for drug bioavailability interactions as a result of inhibition of the phase I drug metabolism enzyme CYP3A4 by resveratrol. No symptom attributed to drug metabolism was observed, and usual medication prescriptions remained unchanged." Likewise in "Resveratrol as an effective adjuvant therapy in the management of rheumatoid arthritis: a clinical study" (Khojah, Ahmed, Abdel-Rahman, & Elhakeim, 2018) uses 1000mg daily while subjects medications include "leflunomide, hydroxychloroquine, sulfasalazine, methotrexate, prednisolone, and various nonsteroidal antiinflammatory drugs" states "RSV dose administered without reported adverse events"

As previously mentioned, RV upregulates ACE2 which has previously been shown to reduce inflammation and may be protective against ARDS. However, since ACE2 is also the binding site for SARS-CoV2, a controversial hypothesis was recently published suggesting that the upregulation of ACE2 by blood pressure medication ACE Inhibitors (ACEI) and Angiotensin Receptor Blockers (ARBs) may increase the risk of infection (Fang, Karakiulakis, & Roth, 2020). This has been countered by a position statement from the European Society of Cardiology (ESC) that states that there is evidence in animal models showing that ACEI and ARBs may be protective in COVID-19 and there are no human evidence showing harm. ESC recommends patients continue ACEI and ARBs (European Society of Cardiology, 2020). There is early evidence is human that ACEI and ARBs may be protective in COVID-19 infection (Sanchis-Gomar F, 2020). On March 17, 2020, the American Heart Association, the Heart Failure Society of America, and the American College of Cardiology put out a joint statement advocating for patients to continue ACEIs and ARBs as prescribed and that changes in medications in the setting of COVID-19 should be completed only after careful assessment (American Heart Association, 2020). More recently ACEI and ARBs use has been associated with improved clinical outcomes in COVID-19 patients (Meng, et al., 2020).

2.3.2 KNOWN POTENTIAL RISKS

There are some concerns of adverse effects based primarily on in vitro studies and animal models (Shaito, et al., 2020). While human clinical trials have shown RV to generally be safe and well tolerated at single oral doses of up to 5g, dose related gastrointestinal upset has been reported (Ramírez-Garza, et al., 2018). High doses are associated with inhibition of cytochrome P450 (specifically CYP3A4, CYP2D6, & CYP2C9), which could result in some drug interactions, most concerning for drugs with a narrow therapeutic window. Drug interactions with nicardipine, warfarin, HIV protease inhibitors, anti-arrhythmics, calcium cancel agonists, antihistamines, and immunosuppressants have been reported in animal models (Shaito, et al., 2020). Hydroxychloroquine and chloroquine, drugs that are being investigated for use in COVID-19, are notably metabolized by CYP2C8 and CYP3A4. RV has been reported to enhance the replication of Hepatitis C virus in vitro (Nakamura, et al., 2010).

Noting that RV is associated with upregulation of ACE2 and ACE2 is the binding site for SARS-CoV2, increased ACE2 may facilitate viral entry into the cell (Yan, Xiao, & Lin, 2020).

2.3.3 KNOWN POTENTIAL BENEFITS

- RV may inhibit binding of SARS-CoV2 to the ACE2 receptor which would inhibit viral entry
- RV inhibits TMPRSS2 which could inhibit viral entry into the cell
- RV may inhibit viral protein synthesis, viral RNA synthesis, and viral productions
- RV increases Nitric Oxide (NO), which may independently inhibit viral replication
- RV may be protective from COVID associated stroke by:
 - inhibits Platelet Activating Factor (PAF)
 - inhibiting complement activation
 - vasoprotective effects of nitric oxide
- RV upregulate ACE2 receptor which has been shown to be protective of lung injury
- RV may protect against the effects of the "cytokine storm" storm of COVID-19 by:
 - Inhibiting TLR4
 - ο Inhibiting NF-κB
 - o Inhibiting IL-6
 - \circ Inhibiting TNF- α
 - Inhibiting CCL5 (RANTES)
 - o Antioxidant effects

2.3.3 ASSESSMENT OF POTENTIAL RISKS AND BENEFITS

The main risk of the proposed treatment in prior human studies is GI upset from resveratrol and a theoretical increase risk of infection by coronavirus. GI upset/diarrhea could lead to dehydration and potentially increased risk of renal injury. This is countered by the multiple mechanisms that could prove beneficial in COVID-19.

3 OBJECTIVES AND ENDPOINTS			
OBJECTIVES	ENDPOINTS	JUSTIFICATION FOR ENDPOINTS	
Primary			
Reduction in hospitalization rates.	21-day hospitalization or death, defined as admission to any hospital for the treatment of COVID-19, or death, within 21 days of randomization for this study (date of randomization = day 0).	Based on reported typical course of illness for COVID-19 most patients will have declared their need for hospitalization in less than 21 days	
Secondary			
invasive ventilation rates, and ECMO usage rates admission to any intensive care unit (ICU) due to worsening symptoms of COVID-19, or death, among patients who are hospitalized within 21 days of randomization (date of randomization = day 0)		Based on reported typical course of illness for COVID-19 most patients will have declared their need for ICU admission/invasive ventilation/ECMO usage in less than 21 days	
Tertiary/Exploratory			
Reduction in morbidity and mortality	Reduction in signs and symptoms based on results of daily surveys. Will also observe mortality rates between groups.	There are mechanisms that would suggest improvements in morbidity and mortality, but this study will likely not have the statistical power to draw firm conclusions.	

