5 STUDY POPULATION

5.1 INCLUSION CRITERIA

The World Health Organization has categorized baseline severity (see table 1). For this study we will be targeting Mild COVID-19 based on their initial ability to be managed as an outpatient and known estimates for admission rates. Patients who test positive but are asymptomatic (such as being tested for contact tracing) will be excluded from the study as there are no defined estimated for admission rates for asymptomatic patients (patients who become symptomatic can be considered for enrollment).

Furthermore, patients age 45 and greater will be selected for this study due to their higher admission rates. In order to be able to detect a difference in treatment efficacy, a population with a higher admission rate is desirable in order keep the sample size (and its associated cost) down. Noting that, in general, the younger population is more social and may have higher rates of infection, but lower rates of admission including younger age patients in the study would likely skew the population to a low hospitalization rate with resultant difficulty detecting a difference between groups. In addition, in order to avoid unnecessary testing and exposure of healthcare workers to patients with COVID-19, pregnancy will be assessed via self-report of pregnancy potential and report of last menstrual period. The risk of pregnancy will be low in this age group.

Patient must test positive for SARS-CoV2 based on an FDA approved test. Due to low false positive rates and to minimize risk to healthcare providers, minimize the use of PPE and discomfort to the patient, repeat confirmatory testing will not be utilized.

- Outpatients in Central Ohio
- Age ≥45 years
- Mild COVID-19 based on WHO Baseline Severity Categorization (see Table 1)
- Symptom duration \leq 7 days
- Patient must have access to the internet or a smartphone to complete surveys
- English-speaking patients

Disease Severity	Description
SARS-CoV-2 Infection	Positive testing by standard reverse transcription polymerase chain
without Symptoms	reaction (RT-PCR) assay or equivalent test
	No Symptom
Mild COVID-19	Positive testing by standard RT-PCR assay or equivalent test
	• Symptoms of mild illness could include fever, cough, sore throat,
	malaise, headache, muscle pain, gastrointestinal symptoms,
	without shortness of breath or dyspnea
	No clinical signs indicative of Moderate, Severe, or Critical Severity

Table 1: Baseline Severity Categorization

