9.2 SAMPLE SIZE DETERMINATION

[figure not shown]
The maximum total number of randomized subjects is capped at 200 by FDA request. We present power analyses of the primary outcome measure (hospitalization) assuming multiple placebo arm

hospitalization rates and effect sizes, as well as for secondary outcome measures. No interim analyses for efficacy are planned, and none are included in the following power calculations.

The primary outcome measure is hospitalization within 21 days of randomization. We provide conservative power estimates by assuming a binary outcome with 5% non-informative loss to follow-up before 21 days. We anticipate this relatively low rate of loss because the endpoint is designed to be evaluable by chart review unless the subject withdraws consent. Hypotheses are as specified in the previous section, and the Z statistic for a two-proportion test is used. The primary Kaplan-Meier analysis will yield slightly better power by treating the outcomes of patients lost to follow-up as censored at the time of last follow-up.

The rate of hospitalization among confirmed cases of COVID-19 ranges between 21% in the 45-54 age bracket, up to 31% for patient's >85 (CDC, 2020). We assumed a mid-point hospitalization rate of 25% for the initial sample size calculation. To achieve 80% power at the 5% two-sided significance level with complete follow-up on 95 subjects per arm with two-sample proportion test, we require a 10% or lower hospitalization rate in the resveratrol arm, compared to a 25% rate in the placebo arm (estimated by power.prop.test, R statistical software). This corresponds to an odds ratio of 1 / 3.

The required resveratrol arm event rate for various placebo arm event rates are plotted in Figure 3. This curve applies to the power for all outcome measures, with lower rates of all secondary outcome events expected to be lower in both arms.

95 complete observations per arm, 80% power

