9.4.2 ANALYSIS OF THE PRIMARY EFFICACY ENDPOINT(S)

The primary efficacy endpoint is hospitalization for any cause within 21 days after randomization, as established by medical record review. Outcomes of subjects who withdraw consent or are otherwise lost to follow-up before 21 days will be considered missing. The intention to treat population for the hospitalization endpoint will be used for analysis. A logistic regression model will be fit with age, sex, race, ethnicity, risk group (see Sec 9.4.7), and randomized group as covariates, with the coefficient to randomized group as the primary estimand. Missing outcome data will be imputed using multiple imputation based on predictions from the logistic regression model of the outcome. Sensitivity analyses will include analyses in which patients lost to follow-up are assumed to not have been hospitalized, and tipping-point analyses systematically and comprehensively varying assumptions about missing outcomes on the treatment and placebo arms independently.

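### Days of symptoms at entry, needed to judge eligibility, are left out of the primary model: a modest gain in efficiency goes unused, with no threat to validity

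*Combined protocol and SAP*

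**What the plan says.** Section 3 counts hospitalization or death within 21 days of randomization, with randomization as day 0. It gives this reason: "Based on reported typical course of illness for COVID-19 most patients will have declared their need for hospitalization in less than 21 days".

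Section 5.1 limits entry by "Symptom duration" to at most 7 days, and section 5.2 excludes asymptomatic patients. Every participant therefore has a symptom onset before entry, somewhere within the preceding week.

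Section 9.4.2 specifies the primary analysis: "A logistic regression model will be fit with age, sex, race, ethnicity, risk group (see Sec 9.4.7), and randomized group as covariates". The coefficient for randomized group is the estimand, and missing outcomes are multiply imputed from the same model. Section 9.4.3 carries this procedure to the secondary endpoints. Symptom days appear in neither section, nor in the subgroup variables of 9.4.7 or the exploratory Cox fits of 9.4.9. Section 4.1 says the allocation list is stratified but names no factors.

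On size, section 9.2 states: "The maximum total number of randomized subjects is capped at 200 by FDA request".

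**The concern.** By the reasoning of section 3, the need for admission shows itself over the course of the illness. A patient who enters on symptom day 7, still mild and without dyspnea, has already passed a week of that course without admission. A patient who enters on day 1 has not. It is plausible, though the documents do not show it, that the first patient's 21-day risk is lower. If so, a predictor that screening must already establish is left in the residual variation.

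The trial has little power to spare. Enrollment is capped, and section 5.1 restricts age partly to keep the sample size down. The question is how much the missing term costs.

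**Working it through.** **1. The plan's own power figure.** Section 9.2 sets the test and its size: "To achieve 80% power at the 5% two-sided significance level with complete follow-up on 95 subjects per arm with two-sample proportion test". The assumed event rates are 25% on placebo and 10% on resveratrol. The 95 comes from 100 randomized per arm after allowing for "5% non-informative loss to follow-up before 21 days", that is 100 × 0.95 = 95. The pooled two-sided Z test gives

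z = [√n·|p₁ − p₂| − 1.96·√(2p̄(1 − p̄))] / √(p₁(1 − p₁) + p₂(1 − p₂)), with p̄ = 0.175

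= [√95 × 0.15 − 1.96 × √0.28875] / √0.2775 = (1.462 − 1.053) / 0.527 = 0.776, so power is 78.1%.

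Exactly 80% power needs a resveratrol rate of 9.7%, which rounds to the stated 10%. The plan's figure is reproduced. Expected events are 95 × (0.25 + 0.10) = 33.

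**2. The window.** Entry at 0 to 7 symptom days plus 21 days of follow-up ends at illness day 21 to 28. No patient is followed to less than illness day 21.

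**3. Power without and with one linear term.** Logistic Wald test, 95 per arm, marginal rates held at 25% and 10%, and 20,000 simulated trials per row. The other 9.4.2 covariates are left out. Two inputs are assumptions because the documents give neither: symptom days uniform on 0 to 7, and the odds ratio per day.

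| Odds ratio per day | Placebo risk, day 0 / day 7 | Power without | Power with | Difference (points) |
|---|---|---|---|---|
| 1.00 | 25.0% / 25.0% | 77.8% | 78.2% | +0.4 |
| 0.90 | 32.2% / 18.5% | 77.7% | 78.6% | +0.9 |
| 0.85 | 36.3% / 15.4% | 77.7% | 78.9% | +1.2 |
| 0.80 | 40.6% / 12.5% | 77.5% | 79.2% | +1.7 |
| 0.75 | 45.1% / 9.9% | 77.7% | 80.4% | +2.7 |
| 0.70 | 49.7% / 7.5% | 77.7% | 81.3% | +3.6 |
| 0.60 | 59.2% / 3.9% | 77.5% | 84.1% | +6.6 |

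The simulation standard error of one power figure is √(0.78 × 0.22 / 20,000), about 0.3 points.

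**4. The same comparison with the 9.4.2 covariates in both models.** Their effects are again assumed.

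- With 4,000 trials per setting: 79.8% v 79.9% at odds ratio 1.0, 80.2% v 81.2% at 0.85, and 78.9% v 81.3% at 0.75.
- With 3,000 trials per setting (log odds of 0.35 per SD of age, 0.6 for risk group, and 0.2 each for sex, race and ethnicity): 78.1% v 77.7% at 1.0, 80.0% v 80.6% at 0.85, and 79.4% v 81.9% at 0.75.

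The largest loss when the covariate is useless is 78.1 − 77.7 = 0.4 points.

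**5. Type I error.** In the 20,000-trial runs it is 4.6% to 5.2% without the term and 4.5% to 5.2% with it.

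**6. Chance imbalance.** For days uniform on 0 to 7, SD = √((8² − 1)/12) = 2.29. The standard error of the between-arm difference in means is 2.29 × √(2/95) = 0.33 day, with a 95% range of ±1.96 × 0.33 = ±0.65 day. An imbalance of one standard error moves the unadjusted risk difference by 0.7 points at odds ratio 0.90 and 1.7 points at 0.75, against a 15-point target.

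**7. A narrower spread of entry days.** If days run from 2 to 7, SD = √((6² − 1)/12) = 1.71 and the 95% range is 1.96 × 1.71 × √(2/95) = ±0.49 day. The simulated gain (6,000 trials, other covariates omitted) falls to 0.7 points at odds ratio 0.85 and 1.4 points at 0.75.

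**The case against.** The case for leaving the plan alone has five parts.

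- **The window is not at fault.** A reader might infer that starting the clock at randomization undercuts the justification in section 3. It does not, because every window covers at least the 21 illness days that section 3 invokes. This stands in full.
- **Imbalance is not a bias.** A reader might infer that a chance difference in symptom days distorts the estimate, or that protection against it has been given up. Such differences are part of the sampling variation that the test and interval already cover, as step 5 shows. The list is also stratified by unnamed factors, so a lack of protection is not established. The omission of names equally means that stratification cannot be credited with balancing symptom days.
- **The gain rests on an assumption.** The documents give neither the strength, the direction nor the shape of the relation. Gains near 3 points need placebo risk to fall from about 45% to 10% across the entry week. Patients are approached only after a positive test and then go through a call, a video and consent, so very early entry may be uncommon. This stands and limits the size.
- **The number may not be recorded.** Eligibility needs only a yes or no at 7 days. The schedule of activities is not legible in the available text, so this cannot be checked. The fix must ask for the number explicitly.
- **A small model is defensible.** With about 33 events, five baseline covariates and possibly several terms for race, restraint is reasonable. One linear term still costs almost nothing in step 4.

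A reader might also infer that the plan misses an effect confined to early starters. Section 2.3.3 lists cytokine and lung-injury mechanisms alongside viral entry and replication, so the documents do not single out early treatment.

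**Conclusion.** The point holds as an optional improvement. Symptom days must be ascertained for eligibility and no planned analysis uses them. Adding them to the primary model is worth about 0 to 3 points of power for an assumed odds ratio per day of 1.0 to 0.75, and less if few patients enter in the first days. Gains of 6 to 7 points appear only at an odds ratio of 0.60, a gradient that nothing in the documents supports. The figures rest on 95 evaluable patients per arm, true rates of 25% and 10%, a linear effect on the log-odds scale, and the assumed spread of entry days.

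Neither the 21-day window nor the type I error is in question.

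**What to change.** Record days from symptom onset to randomization as a number on the eligibility form. In 9.4.2, prespecify it as one linear term in the logistic model. It then also enters the imputation of missing outcomes and, through 9.4.3, the secondary analyses. Naming the stratification factors in section 4.1 or 6.3 would settle whether symptom days are balanced by design.

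The cost is a line of SAP wording, one recorded number and one extra parameter with about 33 expected events. The loss is at most about 0.4 points of power if the covariate is unrelated to outcome. The treatment coefficient becomes conditional on symptom days as well. With marginal rates held at 25% and 10%, the corresponding odds ratio moves from 0.333 at an odds ratio per day of 1.0 to 0.313 at 0.75. For that reason, and so that it does not look data-driven, the term should be fixed before unblinding.

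A continuous treatment-by-days interaction could be added to 9.4.7 as exploratory only. If benefit (10% v 25%) were confined to days 0 to 3, a linear interaction test would have only about 23% power, so a null result would say little.
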